1. INTRODUCTION

1.1 BACKGROUND

According to the Centers for Disease Control (CDC) up to 35% of adults over the age of 20 are obese, meaning they have a body mass index (BMI) of over 30 kg/m² while up to 69% of similarly aged adults are overweight, meaning they have a BMI of 25-30 kg/ m² (1; Appendix 1). Individuals who are overweight or obese are at high risk for adverse impacts to quality of life (QOL) factors including general health (2), pain (3) and psychosocial status (4). However, losing weight via calorie restriction dieting is notoriously difficult for such individuals (2). Sustained loss of even 5-10% of weight is uncommon with most dieters (2,3) with most regaining nearly half of the lost weight after one year (4). While the precise physiological, sociological and genetic factors associated with weight gain and weight loss remain an area of intense investigation, what is becoming clear is that sustained weight loss requires long term calorie intake reduction (2), which, in turn, appears to require, among other factors, appetite control (2,4). The purpose of the present non-significant risk (NSR) study is to investigate the effect of transcutaneous electrical nerve stimulation (TENS) on weight loss in overweight-to moderately (i.e. Type 1) obese individuals (i.e. BMI of 25 to 35 kg/ m² inclusive 15,16; Appendix 1) with a long-term goal of determining if such an approach may be of benefit in assisting such individuals in achieving their weight loss goals.

1.2 PENS AND TENS FOR WEIGHT LOSS

Transcutaneous electrical nerve stimulation (TENS) involving the delivery of electrical current to subcutaneous nerve branches via an electrode placed on the skin surface is a well-established treatment modality for muscle pain, muscle atrophy and spasms as well as for pain associated with a variety of conditions including diabetic neuropathy. More recently this modality has been shown to be effective in treating certain symptoms associated with migraine headaches by delivering electrical stimulation to branches of the trigeminal nerve (8). A related therapy, Percutaneous Electrical Nerve Stimulation (PENS), in which electrode is inserted into the epidermis, is now in general medical usage for the treatment of urinary incontinence, fecal incontinence, and back pain (5-8).

The clinical evidence for a PENS effect on appetite and weight loss is provided by Ruiz-Tovar's study which demonstrated significant weight loss for PENS stimulation of dermatome T6 (the area of skin supplied by cutaneous branches of a single cranial or spinal nerve) via appetite suppression in a European sham control study of 105 subjects (9). Similar preliminary clinical results utilizing TENS have been reported in appetite control and subsequent weight loss by [name], a Stanford University researcher, who was granted a method patent (Transcutaneous Electrical Nerve Stimulator for Appetite Control) for his invention that uses TENS to stimulate the thoracic spine area at T6-T10. Each of these studies utilized obese subjects and provided stimulation only during in-clinic supervised sessions. The present study is designed to extend these preliminary studies by utilizing TENS in overweight-to Type 1 obese-subjects (i.e. BMI of between 25 and 35 kg/ m² inclusive 15,16) stimulating in an outpatient/at home setting using a wearable, patch TENS system.

1.3 THE HYPOTHESIZED MECHANISM OF T6/T7 STIMULATION FOR APPETITE SUPPRESSION AND WEIGHT LOSS

The effect of PENS, and presumably, TENS, has been widely demonstrated by posterior tibial nerve neuro-stimulation in treating urinary and fecal incontinence, creating a somato-autonomic reflex (10,11; Figure 1). The definition of a somato-autonomic reflex is a reflex elicited by stimulation of somatic tissue (strictly speaking, tissue of the musculoskeletal system and the dermis of the skin), and manifesting as an alteration of the autonomic nervous

[figure not shown]

Figure 1: Somato-Autonomic Reflex Arc

system function (Figure 1). Altered autonomic nervous system functions may lead to changes in the function of dependent organs (like the stomach and other gastrointestinal organs), a situation sometimes referred to as a Somato-visceral reflex. To the PI's knowledge, the study cited by Ruiz-Tovar is the first to report using PENS of dermatome T6 to reduce appetite and, consequently, obtain a clinically-significant weight loss⁽⁹⁾. It is likely that the effect is produced by the creation of a Somato-autonomic reflex in similar fashion to percutaneous electrical stimulation of the posterior tibial nerve in treating incontinence, but in this case suppressing appetite⁽¹⁰⁾.

As supported by [name] preliminary results⁽⁹⁾, it is likely that similar results to PENS can be obtained using TENS to stimulate the same region, given the shallow 2 to 4 millimeter depth of sensory afferents throughout the target dermatome. Chen reported that electric gastric stimulation with a gastric pacemaker may affect the central nervous system by segregating hormones in the stomach and regulating satiety and/or appetite, with ghrelin being particularly involved in this mechanism⁽¹¹⁾. As shown by Ruiz-Tovar's study, the electric stimulation's main effect is appetite reduction. This study consisted of 105 subjects divided into 3 groups. Group 1 included 45 subjects who underwent dermatome T6 stimulation and maintained a 1,200 calorie diet and who were scheduled for bariatric surgery. These subjects had BMIs of greater than 40 or greater than 35 with co-morbidities. Group 2 included 45 subjects that maintained a 1,200 calorie diet only and who were scheduled for bariatric surgery. These subjects also had BMIs of greater than 40 or greater than 35 with co-morbidities. Group 3 included 15 subjects with a BMI greater than 30 who received sham stimulation (at the ankle) and who maintained a 1,200 calorie diet. Group 1, the treatment arm, evidenced dietary compliance in excess of 90% and achieved a significant weight loss success (equal to or greater than 5 kilograms (11 pounds) in 76.7% of subjects, as compared to Groups 2 and 3 where weight loss success was less than 6.7% and 0.0%, respectively. No complications were observed associated with the technique.

It thus appears likely that, through safely stimulating T6/T7 via TENS, a Somato-visceral reflex arc will be activated which will suppress appetite and support eventual weight loss in overweight and obese subjects.

2. STUDY RATIONALE

The purpose of the present study is to determine the safety and effectiveness of stimulation via a wearable patch TENS system of the T6/T7 dermatome on appetite suppression in adult (18 to

Protocol #: CD-005; Version #: 4.0

Original Date: May 8, 2018 Revision Date: May 3, 2019

-Confidential-

65 years of age inclusive), overweight/obese subjects (i.e. a BMI of 25 to 35 kg/m² inclusive^{15, 16}; Appendix 1) who desire to lose weight. The study will seek thus to extend existing data on the use of dermatomal stimulation on obese and morbidly obese patient to subjects who are overweight/obese (i.e. a BMI of 25 to 35 kg/m²^{15, 16}; Appendix 1).

2.1 JUSTIFICATION FOR STUDY GIVEN RISK/BENEFIT OUTCOME

Up to 35% of adults over the age of 20 in the United States are overweight. Being overweight places individuals at higher risk for a number of what are termed metabolic disorders including diabetes mellitus. This risk association is thought to be the reason for the high health care costs associated with overweight and obesity. While diet and exercise do show efficacy in a substantial subset of subjects, long term weight control is difficult to achieve for the vast majority of overweight individuals. The physiological and psycho-social reasons for this are not well characterized and likely highly complex, but a key component of this challenge is associated with appetite control. The present study seeks to determine if a method of appetite control utilizing T6/T7 dermatome stimulation in obese individuals can be utilized to the broader overweight population. The study utilizes non-invasive TENS stimulation within the range of the energy delivery well known to be safe for at-home use for nerve and muscle pain. Subjects will be informed of all potential side effects related to stimulation prior to enrollment and, throughout the study, subjects will be monitored and allowed to decrease or discontinue stimulus if any such side effects are deemed to be intolerable for participants.

In addition, since appetite and weight loss can be affected by a variety of physiological and psychosocial factors (^{12,13, 15, 17}), the change in appetite will be measured weekly using a validated tool, the Visual Analog Scale (VAS¹⁴; See Appendix 3) and also assessed at baseline at the end of the study via administration of the Three Factor Eating Questionnaire R-18 V2 (TFEQ-R1V2^{17, 18}). Please note that while the VAS was first developed for pain, it has been validated for weight loss/appetite applications (¹⁴) while the TFEQ-R18V2 has specifically been validated in weight loss applications (^{17, 18}). The present study is not intended to be a formal validation of the assessment tool's applicability to the population targeted by the present study per se; it is intended simply as an assessment of potential changes in such parameters correlated with delivery of therapy during the study. Thus, the use of the tool as presented is considered scientifically valid.

Thus, the non-significant risk of the study is more than balanced by the potential societal benefit of the development of this novel, non-invasive appetite control method.

3. DEVICE DESCRIPTION

The TENS System consists of:

TENS Unit (Appendix 2)	ELIRA wearable Patch
Electronic Diary tool (Appendix 5)	Diary/dietary application running on and Android Smartphone: 4.5" 720p HD TFT display Size (LWH): 2.6 inches, 0.46 inches, 5.1 inches Weight: 4.96 ounces
Device Accessories	Extra packs ELIRA electrodes Device/Phone Chargers Electronic Scale Plastic Phone Cover and System Pack

Protocol #: CD-005; Version #: 4.0

Original Date: May 8, 2018 Revision Date: May 3, 2019

-Confidential-

Other study accessories

TENS Clean-Cote Skin Wipes or **ALCOHOL** prep pads/wipes
Cetaphil Moisturizing Lotion (16oz), and Paper diaries

4. STUDY OBJECTIVES

The objectives of this study are to demonstrate safety and effectiveness of a wearable patch TENS system (Appendix 2) in driving weight loss and appetite suppression when coupled with an integrated weight loss reduction strategy. The study is designed to demonstrate that TENS stimulation sufficient to drive weight loss and appetite suppression is safe and tolerable when compared to standard of care, and that adverse events/adverse device effects are similar to other TENS device use cases.

5. STUDY DESIGN

[figure not shown]
Randomized, adaptive parallel arm study. Subjects will be initially screened during a screening period (1 week, ± 7 days; Figure 2). During this screening period, prior to study procedures being performed, subjects will sign an informed consent form. Then they will have their weight and blood pressure measured, FOCBP will have a pregnancy test, get blood drawn for analysis (blood lipids, HbA1c), and complete patient preference questionnaires. At the end of the screening/baseline period, eligible subjects will be offered the chance to enroll in the study. After enrolling, subjects will be randomized to treatment or control groups.

The Treatment group will be instructed to follow a healthy diet that they will follow for the duration of the study and will receive training on the use of the paper diaries, electronic scale, smartphone app and the Elira wearable patch system. All treatment subjects will be required to stimulate in the office for up to 30minutes to confirm sufficient system training and to acknowledge understanding stimulation settings. A below neck photograph will be taken of the treatment group in requested attire (i.e. biker shorts and sports bra for women, biker shorts for men). Following this, subjects will enter the Therapy Period, for a ~24-week duration. Treatment subjects may be contacted by PI or clinical coordinator to address any questions related to device functionality or compliance. Device usage will be monitored throughout therapy phase to ensure proper functionality and subject safety.

The Control group will be instructed to follow a healthy diet that they will follow for the duration of the study and will receive training on the use of the weekly paper diary and electronic scale. The Control group will not receive the electronic smartphone app or the Elira wearable patch system/components.

At the end of the 3 months of the Therapy Period, all subjects will be assessed for weight loss, blood pressure, blood lipids, HbA1c, and will continue to participate through months 4-6 to confirm the long term safety of the device prior to being terminated from the study. A below neck photograph will also be taken at the 12 week visit.

The Kaplan Meier estimator will be utilized to compare decrease in %Total Body Weight Loss (&TBWL) and appetite scores between treatment and control subjects. Maximum likelihood statistics will be utilized to correct for censoring. Z statistics will be calculated to ensure lack of skewness or curtosis and square root arc sine transformations will be undertaken on the data if required prior to analysis.

Figure 2: Study Outline

5.1 DOSING SCHEDULE

All Treatment Subjects will be trained in required rotation of the patch electrodes every 24h such that it is applied to varying locations on the T6/T7 dermatome. Each active therapy subject will receive up to 40 mA sustained current of stimulation for up to 30 minutes delivered within approximately 30min of meal time (pre-meal breakfast and dinner), not to exceed 75 min daily (including up to 3-5min rescue sessions). Based on tolerance of the therapy, a subject may decrease his or her dose by dropping one of the pre-meal sessions after receiving approval from a clinical coordinator and/or PI. Subjects who do not experience sufficient appetite suppression may also add up to 3 between meal 5min rescue sessions delivered after receiving approval from a clinical coordinator and/or PI. The nominal stimulation dose per day for any subject will thus be 1200 mA (60 minutes at 20 mA) while the maximum dose for any given subject will be 3900 mA (90 minutes at 40 mA and rescue sessions).

During the therapy period, Treatment Subjects will undergo initial assessments to ensure they are familiar with the device, the daily electronic diary, weekly paper diary, and diet options. All subjects (Treatment and Control) will be required to undergo follow-up assessments at least once per every 4 weeks during the study. Additional unscheduled visits per subject will be permitted during the study to address issues related to subject safety. PI and/or clinical coordinator will oversee any adjustments to treatment dosing or stimulation parameters and may contact treatment subjects to address any concerns regarding device functionality.

5.2 DATA COLLECTION:

All subjects will be asked to keep a VAS paper diary (hunger, appetite, weight and diet) in which they will record such values weekly. Subjects will record their diary variables. For treatment

subjects, any adjustments to stimulation session schedule will be recorded within the electronic diary and by clinical coordinators.

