	
The diagram illustrates the study timeline. It begins with a grey bar for 'Screening' at -1 week. This is followed by a red bar for 'Enrollment/Randomization' at Day 0. A long blue bar represents the 'Therapy/Control' phase, spanning from Week 1 to Week 20. The 'End of Study' is marked at Week 24. Key visits are indicated by arrows: Screening (Visit 0) at -1 week, Randomization/Enrollment (Visit 1) at Day 0, Therapy (Visits 2-7) at Weeks 1, 4, 8, 12, 16, and 20, and Control (Visits 2-7) at the same weeks. The End of Study (Visit 8) occurs at Week 24.

Dosing Regime
	
Treatment subjects will be trained in rotation of the patch electrodes every 24h such that it is applied to varying locations on the T6/T7 dermatome. Each treatment subject will receive two treatments of up to 40 mA of sustained current stimulation for 30 minutes each delivered approximately 30 minutes prior to meal times (based on established times set in the smartphone application), not to exceed 75min daily without express consent of PI. Based on tolerance of the therapy, a subject may decrease his/her dose by dropping one of the therapy sessions after receiving approval from a clinical coordinator and/or PI. In addition, subjects who do not experience sufficient appetite suppression may also add up to three 5-minute “on-demand” sessions at 20mA between regular doses after receiving approval from a clinical coordinator and/or PI. The nominal stimulation dose per day for any subject will thus be 1200mA (60 minutes at 20 mA) while the maximum dose for any given subject will be 3000 mA (75 minutes at 40 mA).

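### Section 5.1's maximum daily dose of 3900 implies 105 minutes of stimulation against its own 75-minute cap, and the summary's 3000 does not match its stated schedule either

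*Combined protocol and SAP*

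**What the plan says.** Section 5.1 (Dosing Schedule) describes regular sessions at up to 40 mA, each "up to 30 minutes delivered within approximately 30min of meal time (pre-meal breakfast and dinner", with the daily total "not to exceed 75 min daily (including up to 3-5min rescue sessions". Subjects with too little appetite suppression "may also add up to 3 between meal 5min rescue sessions" once a coordinator or the PI agrees. The paragraph gives a nominal daily dose of 1200 (60 minutes at 20 mA) and then says that "the maximum dose for any given subject will be 3900 mA (90 minutes at 40 mA and rescue sessions". It gives no current for the rescue sessions and no exception to the 75-minute limit.

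The Protocol Summary (Dosing Regime) covers the same ground. It specifies "two treatments of up to 40 mA of sustained current stimulation for 30 minutes each" and up to three 5-minute on-demand "sessions at 20mA between regular doses". Its limit is also 75 minutes a day, but the PI may expressly consent to more. It gives the same nominal dose of 1200, and states that "the maximum dose for any given subject will be 3000 mA (75 minutes at 40 mA".

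**The concern.** These figures are the stated daily exposure limit for an investigational device that subjects use at home for about 24 weeks, at up to 10 centers. Section 5.1 contradicts itself on that limit, and the summary gives a different value for the same quantity. Two sites could read the same protocol and work to different ceilings.

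There is also an effect on the conduct of the study. Section 13.3 classes any departure from authorized device use as a major deviation, and section 8.1.2 keeps subjects with major deviations out of the per-protocol population. A subject who stimulates for 80 to 105 minutes a day breaches one sentence of section 5.1 and complies with another. Deviation grading, and with it per-protocol membership, could therefore differ between sites.

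**Working it through.** **Inputs**

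| Quantity | Section 5.1 | Protocol Summary |
|---|---|---|
| Regular sessions | up to 30 min, breakfast and dinner, up to 40 mA | 2 × 30 min, up to 40 mA |
| Rescue / on-demand | up to 3 × 5 min, current not given | up to 3 × 5 min at 20 mA |
| Daily time limit | 75 min, rescue included | 75 min unless the PI expressly consents |
| Nominal dose | 1200 | 1200 |
| Maximum dose | 3900 | 3000 |

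**Convention.** Dose = minutes × mA, summed over sessions. The nominal dose confirms it: 60 × 20 = 1200. So does the summary's maximum: 75 × 40 = 3000. The unit is therefore mA-min, although both texts label it mA.

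**Reproducing 3900.** Take 90 minutes at 40 mA and three 5-minute rescue sessions at the summary's 20 mA:

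- 90 × 40 + 3 × 5 × 20 = 3600 + 300 = 3900, an exact match.

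Other readings tried do not give 3900:

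- 90 minutes at 40 mA with no rescue: 3600.
- Rescue also at 40 mA: 90 × 40 + 15 × 40 = 4200.
- 90 minutes in total with rescue inside: 75 × 40 + 15 × 20 = 3300.

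**Against the 75-minute cap**

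- Time implied: 90 + 15 = 105 min.
- Excess: 105 − 75 = 30 min, and 30 / 75 = 40%.
- The 90 minutes alone exceed the cap by 15 min, before any rescue session.
- At the highest permitted current throughout, 3900 still needs 3900 / 40 = 97.5 min, which is 22.5 min over.
- 90 / 30 = 3 regular sessions, where both texts provide for two.

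**Against the summary**

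- 3900 − 3000 = 900.
- 3900 / 3000 = 1.30.

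**The summary's 3000 against its own schedule**

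- Time: 2 × 30 + 3 × 5 = 75 min, which fits the cap exactly.
- Dose with rescue at the stated 20 mA: 60 × 40 + 15 × 20 = 2400 + 300 = 2700.
- Dose with rescue at 40 mA: 60 × 40 + 15 × 40 = 3000.

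So 3000 is reached only if the rescue sessions also run at 40 mA, which the summary does not allow. Against 2700, the figure in section 5.1 is 3900 / 2700 = 1.44 times as large.

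**The case against.** The best defence is the summary's consent clause. It shows that the sponsor contemplated more than 75 minutes for some subjects, so 3900 might be a PI-approved ceiling imperfectly carried into section 5.1. This cannot be excluded, and it is a reason not to assume which figure was intended. It does not remove the conflict: section 5.1 has no consent exception, its cap expressly counts rescue sessions, and the summary, which does have the exception, still gives 3000 as the maximum for any subject.

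The second defence is that the practical risk is low, and that stands. The daily total is a derived figure. The rules a site applies session by session largely agree between the two texts. Section 9.12.2 lists frequency, pulse width and amplitude as the programmed settings, and nothing shows a daily mA-min total being programmed. There are also controls: the app works within clinician-set limits, the user manual in Appendix 2 lists an error state for too many sessions, section 5 provides for monitoring of device use, and "PI and/or clinical coordinator will oversee any adjustments to treatment dosing or stimulation parameters". These controls do not say which maximum is right, since the documents give no numeric daily limit built into the device.

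A reader might infer three stronger things that the documents do not support:

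- That subjects received, or would receive, 105 minutes a day. Nothing shows this.
- That 3900 is a miscalculation. The sum is correct; the regimen it describes conflicts with the cap.
- That 3000 is therefore the right value. The stated sessions do not produce it, and no text says which figure is outdated. A leftover three-session regimen would explain the 90 minutes, but that is a guess.

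**Conclusion.** The point holds as an internal inconsistency in a stated exposure limit. Section 5.1's maximum needs 105 minutes against a 75-minute cap, 30 minutes over, and is 1.30 times the summary's maximum. The summary's 3000 is itself 300 above the 2700 that its described sessions can deliver.

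The conflict with the cap rests on section 5.1 alone: 90 minutes exceed 75 whatever the rescue current, and 90 minutes plus three 5-minute sessions make 105. Only the exact decomposition of 3900 and the 2700 depend on the 20 mA rescue current, which is stated in the summary and not in section 5.1.

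The protocol should be corrected, but the practical risk is low. No harm is shown. The sample size and the primary mITT analysis do not depend on these figures; the possible analytic effect is on per-protocol membership through deviation grading.

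**What to change.** 1. Delete the 3900 figure and its bracketed explanation from section 5.1.
2. State one maximum in both section 5.1 and the Protocol Summary, in mA-min:
   - 2700 (60 min at 40 mA plus 15 min at 20 mA) if rescue sessions stay at 20 mA; or
   - 3000 (75 min at 40 mA) only if rescue at up to 40 mA is allowed, with the summary's 20 mA changed to match.
3. State the rescue amplitude in section 5.1.
4. Settle the consent exception: either remove it from the summary, so that 75 minutes is absolute, or put it in both places with an explicit upper limit on minutes and dose that holds even with consent.
5. Before choosing, the sponsor should confirm the intended ceiling and check it against the limits set in the device and app.

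The cost is a text amendment, IRB submission and written approval before implementation (section 13.1), and a notice to sites. The sample size and analysis need no change. If the sponsor did intend to permit 3900, the amendment lowers permitted exposure and should say so.
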